## 6. Research steps

- (1) Patients eligible for inclusion in the study were screened and informed consent was signed.
- (2) Patients were randomly assigned to the experimental group or the control group. Vital signs and hemodynamic parameters were recorded 1 hour before administration, and related indexes such as cardiac function and pulmonary circulation were detected by transesophageal ultrasound, as well as arterial blood gas, central vein blood gas, blood routine, liver and kidney function, electrolyte, myocardial enzyme profile and BNP were detected by blood sampling.
- (3) According to the study protocol, all subjects in the two groups began administration at 8am, and 8am vital signs, arterial blood gas, central vein blood gas,

blood routine, liver and kidney function, electrolytes, myocardial enzyme profile and BNP during medication period and the first 24 hours after medication completion were recorded. The related indexes of cardiac function, pulmonary circulation and hemodynamics were monitored by transesophageal ultrasound. Study withdrawal/early termination: Family members refuse to continue treatment if: Family members withdraw from the study; In the presence of experimental-related serious adverse reactions.

## **7 Evaluation**

### **7.1 Primary and Secondary Endpoints/Outcome Evaluation Primary outcome:**

Rate of RVD at 48h randomized administration. Secondary outcome: 48h after random administration, the following indicators were assessed. Other indicators of right cardiac function were: TAPSE, S', FAC, RVEDA/LVEDA PVR RV-PA coupling CI, SVI, SVR, ScvO2 SOFA score after random 28-day mortality, in-hospital mortality

### **7.2 Safety evaluation**

- (1) Vital signs, physical examination, laboratory examination indicators.
- (2) The incidence of adverse events/adverse reactions was evaluated according to CTCAE4.0 (Annex 4).
- (3) Incidence of serious adverse events/serious adverse reactions.

## **8. Adverse Events and serious adverse events**

Adverse Event Reports: Adverse medical events in patients treated with levosimendan that are not necessarily causal to the treatment.

Reports of serious adverse events: Events requiring hospitalization, prolonged hospitalization, disability, inability to work, life threatening or death occurred during levosimendan treatment. During clinical trials, the clinical investigator is obligated to take necessary measures to ensure the safety of the subjects and record them. In the event of a serious adverse event occurring during a clinical trial, the investigator shall

immediately take appropriate treatment measures for the subject and report to the principal investigator, the Ethics committee of the clinical trial unit, the Food and Drug Administration and the State Food and Drug Administration of the province, municipality or autonomous region, and the sponsor within 24 hours by telephone or fax. At the same time, write a written report to the above institutions within 15 days. The occurrence of serious adverse events must be completed in the CRF Serious Adverse Event Report form.

For all serious adverse events, the investigator should follow up until resolution, recovery to baseline, proven unresolvable/permanent, switch to other treatments, or death. Medical documentation of the serious adverse events, including results of laboratory and auxiliary tests, should be recorded in the original documentation and follow-up form. The investigator and other leaders should analyze and determine cause-and-effect relationships from a clinical perspective for serious adverse events in subjects.

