## **9. Statistical analysis and statistical methods**

- (1) Case enrollment analysis: The total number of enrolled and completed cases in each center was listed, and three analytical data sets (FAS, PPS, SS) were determined. List the cases of shedding and elimination and their causes.
- (2) Demographic data and baseline analysis: descriptive demographic data and other baseline characteristic values; The number of cases, mean value, standard deviation, median, minimum value and maximum value of measurement data were calculated. Count and grade data calculation frequency and component ratio.
- (3) Effect analysis: CMH- $\chi^2$  test considering central effect was used for comparison between groups. t test or Wilcoxon rank sum test were used to compare the measures between groups.  $\chi^2$  test or Fisher's exact probability method were used to compare the classification indexes between groups. Rank data were obtained by Wilcoxon rank sum test or CMH- $\chi^2$  test. Survival data will be described using Kaplan-Meier curves and life tables. A nonparametric confidence interval for the median lifetime is calculated. Linear rank tests (logrank test and Wilcoxon test) were used to compare

survival between the treatment group and the control group. The Cox risk model was used to analyze the potential influence of covariates (predictors). Multivariate logistic regression was used to analyze dichotomous outcomes, such as recurrence rates, and this multivariate model would identify the most significant predictors. Logical or proportional advantage models will be used to adjust for prognostic factors. Precise confidence intervals will be calculated for the binary event incidence.

(4) Safety analysis: the incidence of adverse reactions was calculated; The sub-system lists the frequency and frequency of adverse reactions and calculates the percentage; A detailed list of adverse event cases; A detailed list of adverse event cases; The number and rate of "abnormal normal conversion" or "abnormal intensification" of laboratory indicators, electrocardiogram and physical examination after the test; List laboratory indicators, electrocardiograms, abnormal cases of physical examination and clinical explanations.

(5) Statistical software and general requirements use SAS software for analysis. All statistical tests were two-sided, and  $P \leq 0.05$  would be considered statistically significant.

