## **10. Medical treatment and protection of subjects**

### **10.1 Risk assessment of subjects in the study and risk disposal measures and plans**

(1) Reporting method: Any adverse event, such as the subject's subjective discomfort and abnormal laboratory test, shall be treated seriously, analyzed carefully, and immediately taken measures to protect the safety of the subject.

(2) Processing procedures: record in detail, retest according to the situation, and record its duration, return, disappearance, etc.

(3) Unmitigated adverse events should be followed up, and all adverse events should be followed up until they are properly resolved or stable.

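### Section 8 defines adverse events only for levosimendan patients, and serious ones only during levosimendan treatment, which conflicts with its own reporting text and section 10.1

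*Protocol*

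**What the plan says.** Section 8 of the protocol opens with two definitions. Adverse events are "Adverse medical events in patients treated with levosimendan that are not necessarily causal to the treatment". Serious adverse events are a list of outcomes that ends with "life threatening or death occurred during levosimendan treatment". Section 5.1 gives the control arm 5% glucose and plans a 24 h infusion in both arms.

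Other text is not limited in this way:

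- Section 8, reporting duty: "In the event of a serious adverse event occurring during a clinical trial", the investigator must treat the subject, report within 24 hours and complete the serious event form. The section then requires follow-up of every serious event.
- Section 10.1: any adverse event is to be taken seriously and recorded in detail, and "all adverse events should be followed up until they are properly resolved or stable".
- Section 6: "all subjects in the two groups began administration at 8am", with vital signs and laboratory values recorded during the infusion and for 24 h after it.
- Section 7.2: "The incidence of adverse events/adverse reactions was evaluated according to CTCAE4.0" and "Incidence of serious adverse events/serious adverse reactions", with no arm named.
- Section 9, item (4): "Safety analysis: the incidence of adverse reactions was calculated", again with no arm named. Adverse events themselves are listed there, case by case.

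**The concern.** A definition decides what a site writes on the case report form. If sites apply section 8 as written, an episode of tachycardia or hypotension is an adverse event in one arm and not in the other. Section 1.4.2 names these as the expected drug effects. Patients with ARDS and right ventricular dysfunction can have them without the drug, so only control-arm recording shows the background rate.

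The time limit adds a second gap. The adverse event sentence has no end point, but the serious event sentence has one. A life-threatening event at hour 30 in a levosimendan patient would be an adverse event but not a serious one.

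Event rates recorded on these terms could not be fairly compared between arms. A later analysis plan can reclassify what was recorded, but cannot recover an event that a site left out because the definition told it to.

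**Working it through.** The point rests on wording. The protocol gives no safety figure to reproduce, so the arithmetic below only shows how far each definition reaches.

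**Scope by passage**

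| Place | Arms covered | Time covered |
|---|---|---|
| 8, adverse event definition | levosimendan only | not stated |
| 8, serious event definition | levosimendan only | during treatment (24 h planned) |
| 8, reporting and follow-up | not limited | during the trial |
| 10.1 | not limited | until resolved or stable |
| 6 | both, explicitly | infusion plus 24 h |
| 7.2 and 9(4) | not stated | not stated |

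I read the phrase on levosimendan treatment as governing the whole list of serious outcomes.

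Rows 1 and 2 cannot govern recording together with rows 3 and 4. The clash is direct within section 8 and clear against 10.1. Section 6 sets a measurement schedule and does not call it an adverse event window, so there the definitions are narrower than the planned observation. Sections 7.2 and 9(4) name no population, so they differ in scope but are not contradicted.

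**Inputs**

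- Section 3.2: 23 per arm and 20% dropout. 23 / 0.8 = 28.75, rounded up to 29 per arm; 2 × 29 = 58. The stated size reproduces and is not affected by this point.
- Section 5.1: infusion of 24 h if uninterrupted.
- Section 6: observation of 24 h + 24 h = 48 h.
- Section 2: fixed follow-up of 28 days = 672 h.

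**Reach of the definitions, read literally**

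- Patients within the adverse event definition: 29 / 58 = 50%.
- Hours within the serious event definition, against section 6: 24 / 48 = 50%.
- The same hours against 28 days: 24 / 672 = 3.6%.
- Serious event definition, both limits together: (29 × 24) / (58 × 48) = 696 / 2784 = 25% of scheduled patient-hours.

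**Illustration (assumed risks; the protocol gives none)**

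Expected control patients with an event outside the definition = 29 × risk.

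| Assumed control risk | Expected patients |
|---|---|
| 5% | 1.5 |
| 10% | 2.9 |
| 20% | 5.8 |
| 30% | 8.7 |

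**The case against.** The strongest reply is that the working instructions are not limited by arm. Section 10.1 tells sites to record any adverse event in detail, including discomfort and abnormal laboratory results. Section 8 itself requires a form for a serious event during the trial. Section 6 takes vital signs and laboratory values in both groups, and item (4) of section 9 tabulates laboratory, electrocardiogram and examination changes. Deaths are caught by the 28-day and in-hospital mortality endpoints. A site would have to follow two sentences and ignore the rest. This stands as mitigation: the exposed part is mainly non-fatal clinical events, and whether an abnormal value is classed as an event. It does not settle the conflict, because those duties use the terms that section 8 has just defined narrowly.

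A second reply is that the plan is partly drug-centred by design. The project abstract limits its safety endpoints to severe drug-related reactions, and item (4) calculates incidence for adverse reactions only. This also stands in part. A reader might infer that 7.2 and 9(4) demand event rates from all patients and are therefore contradicted. They do not say so.

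A third reply is that item (4) is descriptive and specifies no between-arm safety test. That is correct, but rates shown for two arms will be compared all the same, and that needs one definition.

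**Conclusion.** The point holds as a conflict of definitions. Two sentences in section 8 exclude the glucose arm, and exclude serious events after the infusion, while the same section's reporting text and section 10.1 do not. This is a wrongly stated rule, not detail left for an analysis plan. It should be corrected, although other text partly mitigates it.

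Literal coverage is half the planned patients and, for serious events, half of the 48 h schedule. These figures describe the wording only and assume an uninterrupted 24 h infusion. The size of any distortion in event rates cannot be computed from the protocol.

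Two stronger readings are not supported:

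- A reader might infer that control-arm events will go unrecorded and that the safety comparison is biased. That depends on sites applying the definitions literally against the broader recording duties.
- A reader might infer from sections 4.5, 6 and 10.2 that stopping study drug means leaving the study and losing the 48 h echocardiography. Section 4.5 turns on completing the observation period, and 10.2 reads most naturally as withdrawal by the patient. What remains is silence on that examination, not a contradiction.

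**What to change.** Reword the two definition sentences in section 8:

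- Define adverse and serious adverse events identically for all randomised subjects in both arms, regardless of causality.
- State one collection window. It must be reconciled with the reporting text, which runs for the duration of the trial, and be no shorter than section 6's infusion plus 24 h. Meeting that minimum alone would not be enough, since a 48 h window could still fall short of the reporting text.
- In item (4) of section 9, tabulate adverse and serious adverse events by arm.

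The cost is a wording change and somewhat more event recording in the control arm and after the infusion. Sample size, examinations and treatment rules are unaffected.

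### Section 8 ties the adverse event and serious adverse event definitions to levosimendan, which read literally leaves out the glucose control arm and contradicts the arm-neutral text in 7.2, 8 and 10.1

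*Protocol*

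**What the plan says.** Section 8 opens with two descriptions that serve as definitions. Adverse event reports cover "Adverse medical events in patients treated with levosimendan that are not necessarily causal to the treatment". Serious adverse event reports cover listed outcomes ending with "life threatening or death occurred during levosimendan treatment". The first is limited by drug received, with no time limit. The second is limited to the period of levosimendan treatment.

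Other text has no arm limit:

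- Later in section 8, the reporting duty begins "In the event of a serious adverse event occurring during a clinical trial", and follow-up applies to every serious adverse event.
- Section 10.1 states "Unmitigated adverse events should be followed up, and all adverse events should be followed up until they are properly resolved or stable".
- Section 7.2 lists as safety measures "The incidence of adverse events/adverse reactions was evaluated according to CTCAE4.0" and "Incidence of serious adverse events/serious adverse reactions".
- Section 6(3) records vital signs and laboratory values in both groups during medication and for the first 24 h afterwards.

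Section 9(4) reads "Safety analysis: the incidence of adverse reactions was calculated; The sub-system lists the frequency and frequency of adverse reactions and calculates the percentage". For adverse events it provides "A detailed list of adverse event cases", and it does not mention serious adverse events. It also gives numbers and rates of laboratory, ECG and examination abnormalities.

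Under section 5.1 the control group receives 5% glucose at 2 ml/h for 24 h. Section 3.2 plans 29 subjects per group.

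**The concern.** A definition of an adverse event decides what is written on the case report form. One that depends on having received levosimendan has no application to a subject on glucose, and one that ends with levosimendan treatment stops labelling events as serious once the infusion is over.

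This matters because the expected harms in section 1.4.2 are a raised heart rate and a fall in blood pressure. Both have many other causes in ventilated ARDS patients, for whom section 5.1 also allows norepinephrine and dobutamine. Causality in a single case is hard to judge, so harm has to be read as a difference between arms in all events. That needs the same definition and the same period in both arms. If control-arm events go unrecorded, levosimendan's harm is overstated. A rate restricted to events judged drug-related would tend to understate it.

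**Working it through.** The point rests on text, so the statements are set side by side first and the few figures follow.

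**Step 1. Scope of each statement**

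| Protocol section | Subject matter | Arm limit | Time limit |
|---|---|---|---|
| 8, first definition | Adverse event reports | Levosimendan only | None |
| 8, second definition | Serious adverse event reports | Levosimendan only | During treatment |
| 8, later text | Duty to report and follow serious events | None | During the trial |
| 10.1 | Handling and follow-up of adverse events | None | Until resolved or stable |
| 7.2 | Incidence of adverse and serious adverse events | None | None |

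The first two rows conflict with the last three. The later rows use the terms that the first two define, so they do not by themselves widen them.

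**Step 2. What the definitions capture if applied literally**

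| Arm and time | Non-serious event | Serious non-fatal event |
|---|---|---|
| Levosimendan, during infusion | Adverse event | Adverse event and serious adverse event |
| Levosimendan, after infusion | Adverse event | Adverse event, serious label lost |
| Glucose, any time | Neither | Neither |

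Deaths at 28 days and in hospital are secondary endpoints in both arms, so later deaths are still counted there.

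**Step 3. Figures**

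- Planned size (section 3.2): 23 / (1 − 0.20) = 28.75, rounded up to 29 per arm; 2 × 29 = 58. The plan's figure reproduces.
- Share outside both definitions: 29 / 58 = 0.50.
- Planned infusion against time to the primary endpoint: 24 h / 48 h = 0.50.
- Planned infusion against 28-day mortality follow-up: 24 / (28 × 24) = 24 / 672 = 0.036, or 3.6%.

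The 50% is simply the allocation ratio, and the two time shares describe a window. None of them measures bias. The 24 h is also only the planned duration, because section 5.1 allows the infusion to be slowed, stopped and restarted at half the dose.

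**Step 4. Effect on the comparison**

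Under the literal reading the control arm has no events to count. If that were reported as zero, the apparent difference would equal the levosimendan-arm incidence, and the error would equal the true control-arm incidence. The protocol gives no such rate, so no number can be attached.

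**Step 5. Section 9(4) against 7.2**

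7.2 names incidence for adverse events/reactions and for serious adverse events/reactions. 9(4) calculates incidence for adverse reactions, gives adverse events a listing, and omits serious events. The term adverse reaction is not defined. If it means drug-related, all-cause adverse events and serious events both lack a rate in 9(4). If it is used for events in general, only the serious-event rate is absent.

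**The case against.** The strongest reply is that both-arm collection is stated often enough for the opening of section 8 to be loose, perhaps translated, wording. Section 6(3) covers both groups, 7.2 has no arm limit, the later text of section 8 requires a form and follow-up for serious events in the trial, 10.1 gives its own arm-neutral examples of an adverse event, and 9(1) sets up a safety set. This largely stands as evidence of intent. It does not remove the conflict. The examples in 10.1 are not a full definition, and a site that looks up what to report finds the narrow wording.

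Three stronger readings are tempting and are not supported:

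- A reader might infer that the trial plans to discard safety data on half its subjects. The arm-neutral sections point the other way; the risk is ambiguity at the sites.
- A reader might infer that non-fatal serious events after the infusion go unrecorded in the levosimendan arm. The adverse event definition has no time limit, so they remain adverse events and lose only the serious label.
- A reader might infer that 9(4) rules out all-cause or serious-event rates. It does not say so, 7.2 already commits to them, and the wording of 9(4) is too loose to bear that weight. The synopsis safety endpoint, which concerns severe drug-related reactions, favours the narrow meaning but does not settle it. 9(4) also gives rates of laboratory, ECG and examination changes that need no causality judgement.

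It can also be said that safety tables belong in a statistical analysis plan. That is fair for 9(4), which is why that part is secondary. It does not answer section 8: who is observed for events, and for how long, governs data collection, and an analysis plan cannot recover events never recorded.

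**Conclusion.** The point holds as a contradiction within the protocol that should be corrected. Read literally, section 8 excludes the control arm (29 of 58 planned subjects) from both definitions and removes the serious label from levosimendan-arm events after the planned 24 h infusion. If sites apply it as written, adverse event and serious adverse event incidence cannot be compared between arms. If they follow 7.2, 10.1 and the later text of section 8, the comparison is sound and only the wording is wrong. The document does not show which rule sites will follow, and it gives no event rates, so the size of any bias cannot be stated.

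The 9(4) mismatch is real but secondary. What survives of it is that 9(4) should match the incidence measures that 7.2 already names.

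**What to change.** **Section 8.** Reword both definitions to cover any adverse medical event, and any event meeting the seriousness criteria, in a subject of either group, from the start of the study infusion (levosimendan or glucose) to one stated time, whether or not causal. The time must be the same in both arms and at least 24 h after the infusion ends, which is when section 6(3) stops recording. At the planned rate that is 24 + 24 = 48 h from the start. Because infusions may be interrupted, a somewhat later fixed time counted from the start is safer than one counted from the actual end.

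**Section 9(4).** Add one line: by arm in the safety set, the number and percentage of patients with any adverse event and with any serious adverse event, with adverse reactions shown as the subset judged drug-related.

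**Optional.** Collecting serious events to day 28 would fit the existing mortality follow-up. Between-arm differences with 95% confidence intervals would help the reader, but neither is needed to remove the contradiction.

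**Cost.** Two sentences and one line. More background intensive-care events will be counted in both arms. Site work increases only if control-arm or post-infusion events are not already being collected.

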## **9. Statistical analysis and statistical methods**

- (1) Case enrollment analysis: The total number of enrolled and completed cases in each center was listed, and three analytical data sets (FAS, PPS, SS) were determined. List the cases of shedding and elimination and their causes.
- (2) Demographic data and baseline analysis: descriptive demographic data and other baseline characteristic values; The number of cases, mean value, standard deviation, median, minimum value and maximum value of measurement data were calculated. Count and grade data calculation frequency and component ratio.
- (3) Effect analysis: CMH- $\chi^2$  test considering central effect was used for comparison between groups. t test or Wilcoxon rank sum test were used to compare the measures between groups.  $\chi^2$  test or Fisher's exact probability method were used to compare the classification indexes between groups. Rank data were obtained by Wilcoxon rank sum test or CMH- $\chi^2$  test. Survival data will be described using Kaplan-Meier curves and life tables. A nonparametric confidence interval for the median lifetime is calculated. Linear rank tests (logrank test and Wilcoxon test) were used to compare

survival between the treatment group and the control group. The Cox risk model was used to analyze the potential influence of covariates (predictors). Multivariate logistic regression was used to analyze dichotomous outcomes, such as recurrence rates, and this multivariate model would identify the most significant predictors. Logical or proportional advantage models will be used to adjust for prognostic factors. Precise confidence intervals will be calculated for the binary event incidence.

(4) Safety analysis: the incidence of adverse reactions was calculated; The sub-system lists the frequency and frequency of adverse reactions and calculates the percentage; A detailed list of adverse event cases; A detailed list of adverse event cases; The number and rate of "abnormal normal conversion" or "abnormal intensification" of laboratory indicators, electrocardiogram and physical examination after the test; List laboratory indicators, electrocardiograms, abnormal cases of physical examination and clinical explanations.

(5) Statistical software and general requirements use SAS software for analysis. All statistical tests were two-sided, and  $P \leq 0.05$  would be considered statistically significant.

